### **9.3 Pharmacokinetic Assessment**

#### **9.3.1 Pharmacokinetic Analysis**

The PK parameter estimates will be determined for Part A using non-compartmental procedures in a validated software program (Phoenix WinNonlin Version 6.4 or later). Samples from Part B

will be stored and will only be sent for bioanalysis at a later date based on immunogenicity or safety results from Part B of the study.

Serum concentrations of LY3074828 will be used to determine the following PK parameters, when possible:

Parameter	Units	Definition
AUC(0-t last )	day* $\mu$ g/mL	area under the concentration versus time curve from time zero to time t, where t is the last time point with a measurable concentration
AUC(0- $\infty$ )	day* $\mu$ g/mL	area under the concentration versus time curve from time zero to infinity
%AUC(t last - $\infty$ )	%	percentage of AUC(0- $\infty$ ) extrapolated
C max	$\mu$ g/mL	maximum observed drug concentration
t max	day	time of maximum observed drug concentration
t 1/2	day	half-life associated with the terminal rate constant ( $\lambda_z$ ) in non-compartmental analysis
CL/F	L/day	apparent total body clearance of drug calculated after extra-vascular administration
V Z/F	L	apparent volume of distribution during the terminal phase after extra-vascular administration
V ss/F	L	apparent volume of distribution at steady state after extra-vascular administration

Additional PK parameters may be calculated, as appropriate. The software and version used for the final analyses will be specified in the CSR. Any exceptions or special handling of data will be clearly documented within the final study report.

Formatting of tables, figures and abbreviations will follow the Eli Lilly Global PK/PD/TS Tool: NON-COMPARTMENTAL PHARMACOKINETIC STYLE GUIDE. The version of the tool effective at the time of PK analysis will be followed.

### General PK Parameter Rules

- Actual sampling times will be used in the final analyses of individual PK parameters, except for non-bolus pre-dose sampling times which will be set to zero.
- Cmax and tmax will be reported from observed values. If Cmax occurs at more than one time point, tmax will be assigned to the first occurrence of Cmax.
- AUC parameters will be calculated using a combination of the linear and logarithmic trapezoidal methods (linear-log trapezoidal rule). The linear trapezoidal method will be applied up to tmax and then the logarithmic trapezoidal method will be used after tmax. The minimum requirement for the calculation of AUC will be the inclusion of at least three

consecutive concentrations above the lower limit of quantification (LLOQ), with at least one of these concentrations following  $C_{\max}$ .

- AUC(0-∞) values where the percentage of the total area extrapolated is more than 20% will be flagged. Any AUC(0-∞) value excluded from summary statistics will be noted in the footnote of the summary table.
- Half-life ( $t_{1/2}$ ) will be calculated, when appropriate, based on the apparent terminal log-linear portion of the concentration-time curve. The start of the terminal elimination phase for each subject will be defined by visual inspection and generally will be the first point at which there is no systematic deviation from the log-linear decline in serum concentrations.  $t_{1/2}$  will only be calculated when a reliable estimate for this parameter can be obtained comprising of at least 3 data points. If  $t_{1/2}$  is estimated over a time window of less than 2 half-lives, the values will be flagged in the data listings. Any  $t_{1/2}$  value excluded from summary statistics will be documented in the footnote of the summary table.
- A uniform weighting scheme will be used in the regression analysis of the terminal log-linear portion of the concentration-time curve.
- The parameters based on the observed last quantifiable drug concentration ( $C_{\text{last}}$ ) will be reported.

### **Individual PK Parameter Rules**

- Only quantifiable concentrations will be used to calculate PK parameters with the exception of special handling of certain concentrations reported below the lower limit of quantitation (BQL). Serum concentrations reported as BQL will be set to a value of zero when all of the following conditions are met:
  - The compound is non-endogenous.
  - The samples are from the initial dose period for a subject or from a subsequent dose period following a suitable wash-out period.
  - The time points occur before the first quantifiable concentration.
- All other BQL concentrations that do not meet the above criteria will be set to missing.
- Also, where two or more consecutive concentrations are BQL towards the end of a profile, the profile will be deemed to have terminated and therefore any further quantifiable concentrations will be set to missing for the calculation of the PK parameters unless it is considered to be a true characteristic of the profile of the drug.

### **Individual Concentration vs. Time Profiles**

- Individual concentrations will be plotted utilizing actual sampling times.

- The terminal point selections will be indicated on a semi-logarithmic plot.

### Average Concentration vs. Time Profiles

- The average concentration profiles will be graphed using scheduled (nominal) sampling times.
- The average concentration profiles will be graphed using arithmetic average concentrations.
- The pre-dose average concentration for single-dose data from non-endogenous compounds will be set to zero. Otherwise, only quantifiable concentrations will be used to calculate average concentrations.
- Concentrations at a sampling time exceeding the sampling time window specified in the protocol, or  $\pm 10\%$ , will be excluded from the average concentration profiles.
- Concentrations excluded from the mean calculation will be documented in the final study report.
- A concentration average will be plotted for a given sampling time only if 2/3 of the individual data at the time point have quantifiable measurements that are within the sampling time window specified in the protocol or  $\pm 10\%$ . An average concentration estimated with less than 2/3 but more than 3 data points may be displayed on the mean concentration plot if determined to be appropriate and will be documented within the final study report.

### Treatment of Outliers during Pharmacokinetic Analysis

Application of this procedure to all PK analyses is not a requirement. Rather, this procedure provides justification for exclusion of data when scientifically appropriate. This procedure describes the methodology for identifying an individual value as an outlier for potential exclusion, but does not require that the value be excluded from analysis. The following methodology will not be used to exclude complete profiles from analysis.

#### Data within an Individual Profile

A value within an individual profile may be excluded from analysis if any of the following criteria are met:

- For PK profiles during single dosing of non-endogenous compounds, the concentration in a pre-dose sample is quantifiable.
- For any questionable datum that does not satisfy the above criteria, the profile will be evaluated and results reported with and without the suspected datum.

#### Data between Individual Profiles

1. If  $n < 6$ , then the dataset is too small to conduct a reliable range test. Data will be analyzed with and without the atypical value, and both sets of results will be reported.
2. If  $n \geq 6$ , then an objective outlier test will be used to compare the atypical value to other values included in that calculation:
  - a. Transform all values in the calculation to the logarithmic domain.
  - b. Find the most extreme value from the arithmetic mean of the log transformed values and exclude that value from the dataset.
  - c. Calculate the lower and upper bounds of the range defined by the arithmetic mean  $\pm 3*SD$  of the remaining log-transformed values.
  - d. If the extreme value is within the range of arithmetic mean  $\pm 3*SD$ , then it is not an outlier and will be retained in the dataset.
  - e. If the extreme value is outside the range of arithmetic mean  $\pm 3*SD$ , then it is an outlier and will be excluded from analysis.

If the remaining dataset contains another atypical datum suspected to be an outlier and  $n \geq 6$  following the exclusion, then repeat step 2 above. This evaluation may be repeated as many times as necessary, excluding only one suspected outlier in each iteration, until all data remaining in the dataset fall within the range of arithmetic mean  $\pm 3*SD$  of the log-transformed values.

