#### Reporting of Excluded Values

Individual values excluded as outliers will be documented in the final report. Approval of the final report will connote approval of the exclusion.

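### SAP 9.3.1 allows a single primary PK value, chiefly Cmax, to be excluded for its size alone, and at 16 to 18 per arm does not require the ratio with and without it

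*SAP*

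**What the plan says.** The outlier text in SAP 9.3.1 has an introduction, two branches and a reporting rule.

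- **Introduction (Treatment of Outliers during Pharmacokinetic Analysis).** Use is optional: "this procedure provides justification for exclusion of data when scientifically appropriate". No criterion for that judgement follows. The method identifies a candidate "but does not require that the value be excluded from analysis". One limit is set: "The following methodology will not be used to exclude complete profiles from analysis".
- **Within one subject's profile.** A quantifiable pre-dose concentration may be excluded outright. For any other questionable point, "the profile will be evaluated and results reported with and without the suspected datum".
- **Between subjects, fewer than six values.** "Data will be analyzed with and without the atypical value, and both sets of results will be reported".
- **Between subjects, six or more values.** A test is used to "compare the atypical value to other values included in that calculation". The most extreme log value is set against the mean ± 3 SD of the remaining ones. If it falls outside, "then it is an outlier and will be excluded from analysis". The step may be repeated while at least six values remain. This branch has no with-and-without requirement.
- **Reporting.** "Individual values excluded as outliers will be documented in the final report". SAP 9.3.1 also requires special handling to be documented, and SAP 9.1 lists all databased data.

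SAP 9.3.2 gives the primary model: log AUC(0-∞), AUC(0-tlast) and Cmax, arm as the only fixed effect, Test 1/Reference ratio with a 90% CI. It neither invokes nor excludes the outlier procedure. Protocol section 10.3 has no outlier rule, and SAP section 11 records no change from the protocol.

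**The concern.** Part A bridges two 1-mL injections to one 2-mL injection (Protocol 3.1). No equivalence limit is set, so the ratio and its 90% CI are the result. An unexplained low value after the single 2-mL injection bears directly on that question.

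The 3-SD limit is fixed in advance, but the decision to run the test and act on it is not. That decision can be made with the values in view and without any identified error. Protocol 5.4 justifies open-label conduct on the ground that PK endpoints are not open to bias, and a discretionary exclusion after the data are seen weakens that argument.

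The SAP accepts with-and-without reporting as the safeguard for small datasets and for most questionable points within a profile. It omits it in the one branch that Part A, with 16 to 18 per arm, will use.

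**Working it through.** **Inputs.** 18 randomised and 16 completing per arm; CV 49% for both AUCs and 23% for Cmax (SAP section 7). The CVs come from a single 120-mg SC dose, which Protocol 3.2 says 5 healthy subjects received. They are scenarios rather than firm estimates.

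**Log-scale SD.** SD = sqrt(ln(1 + CV²)), giving 0.464 at CV 49% and 0.227 at CV 23%. As a check on these inputs, t(0.95, 30) × 0.464 × sqrt(2/16) = 0.278, in line with the plan's 0.28 taken as a half-width at the assumed SD. The probability and the subject total attached to that 0.28 are a separate matter. The plan gives no error rate for the outlier rule, so there is none to reproduce.

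**Chance of flagging a valid value.** For normal log data, the distance of one value from the mean of the others, divided by their SD and by sqrt(1 + 1/(n−1)), follows t with n−2 degrees of freedom.

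- By arm, n = 16: 3/sqrt(16/15) = 2.905; two-sided p on 14 df = 0.01153; × 16 = 0.185 per arm at most. Two arms: 1 − (1 − 0.185)² ≈ 0.336.
- Pooled, n = 32: 3/sqrt(32/31) = 2.953; p on 30 df = 0.00607; × 32 = 0.194 at most.

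Simulation of the rule with iteration agrees (20,000 trials, log-normal data, no true outliers, test always run and acted on, one parameter):

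| Setting | Trials losing a value | 90% CI coverage, all values → after rule |
|---|---|---|
| CV 49%, n = 16, by arm | 33.4% | 0.901 → 0.870 |
| CV 49%, n = 16, pooled | 19.1% | 0.901 → 0.900 |
| CV 23%, n = 16, by arm | 33.3% | 0.898 → 0.868 |
| CV 23%, n = 16, pooled | 18.9% | 0.899 → 0.898 |

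At 18 per arm (CV 23%), removal is 32.7% by arm (coverage 0.874) and 20.3% pooled (0.902).

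**One low Test 1 value.** Multiply one of 16 values by a factor f. It moves by ln(f), and the ratio with all values kept becomes exp(ln(f)/16). For f = 0.3, ln(f) = −1.204. That is 1.204/0.227 = 5.3 SD for Cmax but 1.204/0.464 = 2.6 SD for AUC, and the ratio is exp(−1.204/16) = 0.93. Removal rates (by arm / pooled) and mean ratios (all values → after rule), from 10,000 trials each:

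| f (assumed) | Cmax removed | Cmax ratio | AUC removed | AUC ratio |
|---|---|---|---|---|
| 0.1 | 100% / 100% | 0.87 → 1.00 | 95.8% / 96.8% | 0.87 → 1.00 |
| 0.3 | 97.6% / 98.4% | 0.93 → 1.00 | 40.3% / 37.7% | 0.93 → 0.96 |
| 0.5 | 55.1% / 54.4% | 0.96 → 0.99 | 11.2% / 9.6% | 0.96 → 0.97 |
| 0.7 | 13.3% / 10.1% | 0.98 → – | 3.7% / 2.5% | 0.98 → – |

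The 0.98 is exp(ln(0.7)/16); the mean after the rule was not tabulated for that row. Where the Cmax value at f = 0.3 is removed, the average lower 90% limit moves from 0.77 to 0.88 by arm (0.87 pooled).

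**The case against.** The strongest reply is that this is an optional, documented procedure with a fixed limit in a Phase 1 study. Much of that stands, and it limits what can be claimed.

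- **A reader might infer that a third of trials will lose valid data.** The documents do not support that. The test starts from a value thought atypical, and the rates above assume that it is always run and acted on. If the option is not used the effect is nil, and pooled use costs essentially no coverage.
- **A reader might infer that a subject with a failed injection would vanish from every primary ratio.** The bar on excluding complete profiles probably prevents this, because such a failure lowers both AUCs and Cmax together. The gap is one parameter going while the others stay. In a joint simulation at 30% of expected exposure, with an assumed log-scale correlation of 0.5 or 0.8, Cmax was removed and AUC kept in about 58% of trials.
- **A reader might infer that the all-values ratio will not be shown.** SAP section 3 puts the detailed table descriptions in a separate shell document that is not available here. Only the SAP text can be judged, and it does not require that ratio. Documented exclusions and full listings would let a reader recompute it.
- **A reader might see a contradiction between optional exclusion and the mandatory wording of step 2e.** It reads more naturally as optional use followed by a fixed algorithm. That is an editorial matter.
- **Application to the primary parameters is inferred.** The between-subject text names no parameter, and SAP 9.3.2 does not invoke it. Equally, nothing exempts AUC or Cmax, and SAP 9.3.2 analyses the values that SAP 9.3.1 produces.

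None of this supplies a criterion for the judgement, a with-and-without result at six or more values, or the choice between by-arm and pooled use.

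**Conclusion.** The concern holds in limited form. The SAP permits, but does not require, an individual between-subject PK value to be excluded on extremeness alone after the data are seen. The primary parameters are not exempted. At the planned sample size the text does not require the ratio with and without the value, and the reference set for the test is unstated.

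The size runs from nothing, if the option is not used, to the upper case in the tables. For Cmax the rule can remove a partly reduced exposure: about 98%, 54–55% and 10–13% of trials at 30%, 50% and 70% of expected. For AUC the figures are about 38–40%, 10–11% and 3–4%, so the effect is large mainly when delivery nearly fails, which is where the bar on excluding complete profiles is most likely to apply. These figures assume log-normal data, 16 per arm, one parameter at a time, assumed exposure levels, and CVs from 5 subjects.

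**What to change.** Amend the SAP as follows.

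- (a) In 9.3.2, state that the primary analysis of AUC(0-∞), AUC(0-tlast) and Cmax keeps all evaluable values. A value is removed only for a documented assay, sampling or dosing error, not for its size alone. An extreme value may prompt the check. Define evaluable, since SAP section 8 uses the term without a definition.
- (b) Where the 3-SD test flags a value, report the ratio and 90% CI without it as a sensitivity analysis beside the all-values result.
- (c) State whether the test is run by arm or pooled, noting that by-arm use lowers coverage.
- (d) Align the wording of step 2e with the introduction (editorial).

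The cost is SAP wording, one extra table, and a wider primary interval when an extreme value is genuine. In the simulation the log-scale half-width with all values kept was about 39–40% larger than under the rule for a Cmax value at 30% (1/0.721 to 1/0.714), and about 34–35% larger for an AUC value at 10% (1/0.746 to 1/0.739).

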#### Reporting of Excluded Values

Individual values excluded as outliers will be documented in the final report. Approval of the final report will connote approval of the exclusion.

#### **9.3.2 Pharmacokinetic Statistical Methodology**

For Part A, the  $AUC(0-\infty)$ ,  $AUC(0-t_{last})$ , and  $C_{max}$  will be log-transformed and analyzed using a linear fixed-effects model. The model will include dosing regimen arm as a fixed effect. The dosing regimen differences between the Test 1 arm and the Reference arm will be back-transformed to present the ratios of geometric least squares means and the corresponding 90% CI.

Example SAS code:

```
proc mixed data=xxx;
  by parameter;
  class arm;
  model log_pk = arm / residual;
  lsmeans arm / alpha=0.1 cl pdiff;
  ods output lsmeans=lsmeans;
  ods output diff=diffs;
```

**run;**

The  $t_{max}$  of LY3074828 between the 1 x 2-mL PFS (Test 1) and the 2 x 1-mL PFS (Reference) will be analyzed using a Wilcoxon rank sum test for Part A. Estimates of the median difference, 90% CIs, and p-values from the Wilcoxon rank sum test will be calculated.

Additional PK analyses may be conducted for Part A if deemed appropriate.

## **9.4 Safety and Tolerability Assessments**

### **9.4.1 Adverse events**

Where changes in severity are recorded in the Case Report Form (CRF), each separate severity of the AE will be reported in the listings, only the most severe will be used in the summary tables. A pre-existing condition is defined as an AE that starts before the subject has provided written informed consent and is ongoing at consent. A non-treatment emergent AE is defined as an AE which starts after informed consent but prior to dosing. A treatment-emergent AE is defined as an AE which occurs postdose or which is present prior to dosing and becomes more severe postdose.

All AEs will be listed. Treatment-emergent AEs will be summarized by treatment, severity and relationship to the study drug. The frequency (the number of AEs, the number of subjects experiencing an AE and the percentage of subjects experiencing an AE) of treatment-emergent AEs will be summarized by treatment, Medical Dictionary for Regulatory Activities (MedDRA) version 20.1 system organ class and preferred term. The summary and frequency AE tables will be presented for all causalities and those considered related to the study drug. Any serious AEs will be tabulated.

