#### 3.2. Background

LY3074828 is a humanized immunoglobulin G4-variant monoclonal antibody that is directed against the p19 subunit of interleukin-23 (IL-23) and does not bind interleukin-12. LY3074828 is being developed for the treatment of autoimmune diseases in which the IL-23 pathway is thought to have a significant pathogenic role. Neutralization of IL-23 with an anti-mouse IL-23 surrogate antibody (directed against the p19 subunit) significantly reduced the development of arthritis and inhibited ileal inflammation in a mouse model of spondyloarthropathy with bowel inflammation (Ruutu et al. 2012). Additionally, neutralization of IL-23 significantly reduced the disease score in the relapsing-remitting experimental autoimmune encephalomyelitis (multiple sclerosis-like) model in mice. Anti-IL-23 antibody also demonstrated some efficacy in preclinical arthritis models, depending on the timing of intervention (Cornelissen et al. 2013).

LY3074828 has been evaluated in 5 healthy subjects (single 120-mg SC doses) and in 33 subjects with plaque psoriasis (single ascending intravenous [IV] doses of 5, 20, 60, 120, 200, 350, or 600 mg) in Study I6T-MC-AMAA (AMAA). Furthermore, 43 healthy Japanese and Caucasian subjects were administered single IV doses of 60, 200, 600, or 1200 mg LY3074828, or placebo, or single SC doses of 200 mg LY3074828, or placebo, in Study I6T-MC-AMAD (AMAD).

No serious adverse events (SAEs) were reported in either study. There were no drug-related treatment-emergent adverse events (TEAEs) of National Cancer Institute Common Terminology Criteria for Adverse Events Grade 2 or higher reported in Study AMAA, and no infusion reactions, injection-site reactions, or adverse events (AEs) considered related to study drug were reported in Study AMAD. There were no dose-dependent trends in AEs, or clinically important changes in vital signs, electrocardiograms (ECGs), or clinical laboratory results across both studies that were considered to be related to the study drug. Pharmacokinetic results obtained

from Study AMAA indicated that serum exposure of LY3074828 increases in a dose-proportional manner, and that the mean half-life associated with the terminal rate constant ( $t_{1/2}$ ) was 10.5 days, which did not appear to be dependent on dose. Maximum concentrations were observed 3 days postdose following SC administration and, based on the area under the concentration versus time curve (AUC), the SC bioavailability was 40%.

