**Table AMAQ.1. Objectives and Endpoints**

Objectives	Endpoints
Primary	
Part A 
 
To evaluate the PK of LY3074828 solution formulation after administration of 250-mg doses using 2 x 1-mL and 1 x 2-mL PFS injections in healthy subjects.
 
To assess the safety and tolerability of, and pain associated with, LY3074828 PFS administrations in healthy subjects.
 
	Part A 
 
The primary PK endpoints will be the <math>C_{max}</math>, <math>AUC(0-t_{last})</math>, and <math>AUC(0-\infty)</math> of LY3074828.
 
Incidence of TEAEs.
 
SF-MPQ, including VAS pain score.
 

Part B 
 
To compare the safety and tolerability of, and pain associated with, LY3074828 solution formulation after administration of 125- and 250-mg doses using 1-mL AI and 2-mL AI SC injections with different injection speeds (slow and fast) in healthy subjects.
 
	Part B 
 
Incidence of TEAEs.
 
SF-MPQ, including VAS pain score.
 

Abbreviations: AI = autoinjector;  $AUC(0-\infty)$  = area under the concentration versus time curve from time zero to infinity;  $AUC(0-t_{last})$  = area under the concentration versus time curve from time zero to time  $t$ , where  $t$  is the last sample with a measurable concentration;  $C_{max}$  = maximum observed drug concentration; PFS = pre-filled syringe; PK = pharmacokinetic; SC = subcutaneous; SF-MPQ = Short Form McGill Pain Questionnaire; TEAE = treatment-emergent adverse event; VAS = visual analog scale.

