## 5.4. Scientific Rationale for Study Design

Conducting the study in healthy subjects mitigates the potential confounding effects of the disease state and concomitant medications in patients. Healthy subjects are frequently used in the assessment of bioavailability of both small and large molecules.

For Part A, single doses of LY3074828 and the PK sampling time points have been selected to generate PK profiles sufficient to fulfill the study objectives. As the primary endpoints for Part A of this study are PK-related and are not subject to bias, it is not considered necessary for this study to be blinded. Subjects and site staff will be aware of the administration route and treatment.

For Part B, only an evaluation of safety and tolerability of, and pain associated with, the investigational AI administrations is intended. Pharmacokinetic samples are collected only in conjunction with immunogenicity samples to provide concentrations of LY3074828 to aid in the interpretation of ADA data if needed.

For Part A, a parallel-group design was chosen because a crossover design is impractical for compounds that have long half-lives, such as monoclonal antibodies. Additionally, a crossover study design could confound PK data if subjects develop neutralizing ADAs.

For Part B, a crossover design was chosen as PK analysis is not an endpoint and a relatively short time between injections will allow a more accurate comparison of injection-site pain by subjects

Monoclonal antibody therapy has been associated with hypersensitivity reactions, including injection-site reactions. Follow-up details on injection-site reactions will be collected by the investigative site regarding the severity, duration, type, and timing of the start of the event in relation to the start of study drug administration in order to further characterize these events.

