#### **9.4.4.2. Injection Instructions**

Prior to the PFS or AI injection, the investigator or his/her designee will prepare the subject's skin. The injections will be given according to the instructions provided by the sponsor.

Pre-filled syringe injections into the abdomen will be administered by investigative site staff. All subjects will receive training on how to use the AI to self-administer into the abdomen. The investigator or his/her designee will answer any questions the subject may have and will demonstrate the steps required for injection according to the IFU. Subjects will be monitored while using the AI to ensure successful self-injections. Investigative site staff who observe the subject's self-injection with the AI will fill out the AI Use Assessment Questionnaire. All study injection sites will be marked using a template for size and with a surgical marker in order to identify study injection sites for later assessments.

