Given that the subjects have only a single exposure to LY3074828 in Part A, and only 2 doses over an approximately 24-hour period in Part B, any ADA response is anticipated to peak and then diminish due to lack of additional exposures. Subjects will have ADA sampling at baseline (predose) and Days 15, 29, 57, and 85 in Part A, and at baseline (predose) and Days 15, 43, and 86 in Part B. Subjects that are observed to have a titer greater than 1:1000, or non-decreasing titers that meet the definition of TE-ADA, will be requested to return every 3 months after the last sample to have follow-up ADA samples tested until the titer has returned to within 1 titer of their baseline or is clearly trending back to the baseline titer. The rationale for the definitions of both TE-ADA and return to baseline is based on the premise that a 1-titer change may result from expected assay variability.

Subjects followed for at least 1 year since last dose who have not returned to baseline, as defined above, will be assessed for safety concerns and, if no clinical sequelae are recognized by the clinical team, no further follow-up will be required. Subjects who have clinical sequelae that are considered potentially related to the presence of TE-ADA may also be asked to return for additional follow-up testing.

Samples will be retained for a maximum of 15 years after the last subject visit, or for a shorter period if local regulations and the institutional review board (IRB) allow, at a facility selected by the sponsor. The duration allows the sponsor to respond to future regulatory requests related to the IPs. Any samples remaining after 15 years will be destroyed.

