## 6. TREATMENTS

The following is a list of the study treatment abbreviations that will be used in the TFLs.

Part	Study Treatment Name	Abbreviation	Treatment order in TFL
A	250 mg LY3074828 PFS (2 x 1 mL)	Reference	1
	250 mg LY3074828 PFS (1 x 2 mL)	Test 1	2
B	250 mg LY3074828 AI (1 x 2 mL) [Slow]	Test 2	3
	250 mg LY3074828 AI (1 x 2 mL) [Fast]	Test 3	4
	125 mg LY3074828 AI (1 x 1 mL) [Slow]	Test 4	5
	125 mg LY3074828 AI (1 x 1 mL) [Fast]	Test 5	6

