### **9.4.3 Clinical laboratory parameters**

All clinical chemistry and hematology data will be summarized by parameter and treatment, and listed. Urinalysis data will be listed. Additionally clinical chemistry, hematology and urinalysis data outside the reference ranges will be listed.

Values for any clinical chemistry, hematology and urinalysis values outside the reference ranges will be flagged on the individual subject data listings.

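### Part B tabulates TEAEs and laboratory data by injection speed although every subject has had both speeds by Day 2; a cheap, descriptive-only layout fix

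*SAP*

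**What the plan says.** The Part B primary objective (Protocol Table AMAQ.1) is to compare safety and tolerability, and pain, "using 1-mL AI and 2-mL AI SC injections with different injection speeds (slow and fast) in healthy subjects". Incidence of TEAEs is one of its endpoints.

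SAP 6 lists the treatment labels for the tables, figures and listings. In Part B each label is one device at one speed, for example "250 mg LY3074828 AI (1 x 2 mL) [Slow"; there is no label for both speeds combined or for sequence. SAP 9.4.1 then says: "Treatment-emergent AEs will be summarized by treatment, severity and relationship to the study drug". SAP 9.4.3 says: "All clinical chemistry and hematology data will be summarized by parameter and treatment, and listed".

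SAP 9.4.1 counts as treatment-emergent any AE that starts or worsens after dosing. It sets no time window and does not say to which of two doses an event belongs. The protocol describes the exposure as "only 2 doses over an approximately 24-hour period in Part B".

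**The concern.** A by-speed column is meaningful only if what is counted in it can be traced to that speed. In Part A each subject has one regimen, so the by-treatment layout works. In Part B the subject crosses from one speed to the other after a day, and nearly all follow-up comes after both. Whoever programs the table must place a headache on Day 20 under slow, fast or both, and the SAP gives no rule. The choice can change the appearance of a primary endpoint table, and it might be made after the data are seen.

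At stake is how readable the slow-versus-fast safety comparison is. Later events that say nothing about speed are mixed with the early events that may.

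**Working it through.** **Timing (Protocol 5.1, 9.6.1 and the Part B Schedule of Activities)**

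- Day 1 to Day 86 is 85 days; Day 2 to Day 86 is 84 days. 84/85 = 98.8% of follow-up comes after both injections.
- Chemistry and hematology are scheduled at screening, Day -1 and Days 15, 43 and 86. So 3 of 3 post-dose visits come after both speeds, and none falls between the injections.
- Protocol 3.2 reports that "Maximum concentrations were observed 3 days postdose following SC administration", with a half-life of 10.5 days. Systemic exposure from both doses therefore peaks after the second injection, without washout.

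**Laboratory data.** If each value is entered under both speeds, the two columns are identical. If it is entered under the last speed, the columns compare the slow/fast and fast/slow sequences, and both groups have had both speeds. Neither layout shows an effect of speed.

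**TEAEs, an illustration.** The documents give no event rates, so these are assumptions: probability of a TEAE within 24 hours of injection aS = 5% (slow) and aF = 25% (fast), so D = 20 points; probability of a later TEAE L = 40%; all independent; 18 subjects per arm (Protocol 10.1), 9 per sequence. The measure is the percentage of subjects with any TEAE.

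1. Per-injection windows: 25 − 5 = **20 points**.
2. Later events to the last speed. A subject's last speed shows 1 − (1 − a)(1 − L), and the first speed shows a.
   - Slow: 1 − 0.95 × 0.60 = 43%; (5 + 43)/2 = 24%.
   - Fast: 1 − 0.75 × 0.60 = 55%; (25 + 55)/2 = 40%.
   - Gap **16 points**; in general D(1 − L/2).
3. Later events under both speeds: 43% against 55%, gap **12 points**; in general D(1 − L).

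| Later-event rate L | Windows | Last speed | Both speeds |
|---|---|---|---|
| 20% | 20 | 18 | 16 |
| 40% | 20 | 16 | 12 |
| 60% | 20 | 14 | 8 |

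In 200,000 simulated trials at L = 40%, the chance that the table shows no gap or the wrong direction is about 6% (windows), 18% (last speed) and 15% (both speeds). For the wrong direction alone it is about 2%, 9% and 4%.

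The dilution arises because a subject is counted once. In the number of AEs, which SAP 9.4.1 also reports, rules 2 and 3 leave the expected difference at D, and later events only add noise.

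**What is not affected.** Pain, injection duration and the scheduled site assessments are recorded separately for each injection (Part B Schedule of Activities; SAP 9.4.7 to 9.4.9). Injection-site AEs can also be traced, because sites are marked "with a surgical marker in order to identify study injection sites for later assessments".

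**The case against.** The strongest reply is that the plan already handles the comparison that matters. Protocol 3.1 says the autoinjectors are evaluated mainly for pain and injection-site reactions, and scheduled assessments of both are tied to one injection. What remains is late non-local events and laboratory values, where an effect of injecting over 13 rather than 5 seconds, or 7 rather than 4.5, is least plausible. This stands, and it is the main reason the point is minor.

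Sequence is randomized, so placing later events under the last speed or under both does not favor either speed. This stands too: the effect is noise and shrinkage toward no difference.

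SAP 9.4.1 also requires tables limited to events considered related to study drug, which would remove some unrelated later events. This helps in part, but relatedness to the drug does not say which of two injections of that drug was responsible.

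SAP 3 leaves table detail to a separate shell document, which was not available here and may hold a placement rule. It is therefore not established that the tables will be diluted, only that the layout as written allows it. SAP 6 does fix the labels, and they include no pooled column.

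Finally, the 5% and 25% rates are assumed. Protocol 3.2 reports no injection-site reactions and no drug-related AEs in Study AMAD, so a 20-point gap is not a forecast.

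**Conclusion.** The point holds as a cheap improvement to descriptive tables. By-speed laboratory columns in Part B carry no speed information; this follows from the visit schedule alone. By-speed TEAE percentages can understate a speed difference. With the assumed rates, 20 points would show as 16 or 12, and over later-event rates of 20% to 60% as 18 to 14 or 16 to 8, depending on the placement rule. These sizes rest on the assumed rates, on independence and on later events being unrelated to speed.

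Two stronger readings do not hold. A reader might infer that the Part B comparison is invalid or that an error rate changes. SAP 9.4.13 plans no inferential safety analysis, and the modelled pain comparison uses per-injection scores. A reader might also expect a far larger dilution, to 6 points. That needs a different rule, in which everything after an injection, including the second injection's early events, is counted under that injection. The first injection's column then shows 1 − 0.95 × 0.75 × 0.60 = 57.25% in either sequence, so slow is (57.25 + 43)/2 = 50.1%, fast is (57.25 + 55)/2 = 56.1%, and the gap is 6 points. The SAP does not state that rule.

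**What to change.** Add a Part B paragraph to SAP 9.4.1 and 9.4.3:

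1. Compare slow and fast on TEAEs with onset within 24 hours after each injection, ending at the second injection for the Day 1 dose.
2. Assign injection-site AEs, whenever they start, to the injection given at that marked site.
3. Summarize all later non-local TEAEs, and the Day 15, 43 and 86 laboratory data, by autoinjector arm (2-mL, 1-mL) with speeds combined.

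If the table shells already contain such a rule, state it in the SAP.

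The cost is one paragraph and a table layout, with no change to dosing, visits or sample size. Dose times are recorded (Protocol 7.2.1), and for injection-site reactions the site collects the "timing of the start of the event in relation to the start of study drug administration" (Protocol 5.4). That onset times exist for other AEs is an assumption to confirm.

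The downsides are small. Late non-local events are no longer shown by speed, but the one-day spacing cannot support that anyway. The 24-hour window comes from the dose spacing, not from a documented risk period. The window after the Day 2 injection also contains Day 1 drug, which the randomized sequence balances between speeds.
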